5.0 STUDY DESIGN

This will be a multi-center prospective, randomized, controlled study with EBV treatment statistically evaluated using Intent-to-Treat (ITT) analyses. Random assignment will be conducted using an allocation ratio of 2:1; two study participants will be randomized to the EBV Treatment arm for every one participant randomized to the Control arm. A maximum of 183 patients with severe heterogeneous emphysema, who meet study entry criteria, consisting of screening eligibility criteria, baseline eligibility criteria, and procedure eligibility criteria, will be enrolled. Safety and effectiveness of BLVR using the Pulmonx EBV will be evaluated at 1 year. For study participants who have been treated with EBV, a secondary intervention such as valve removal, replacement, or adjustment, as described in this protocol, may be considered during the study follow-up. Long-term data will be collected annually through 5 years. Per the regulatory plan agreed to with FDA, 1 year of follow-up is required pre-approval and the remaining 4 years of follow-up will be conducted post-approval. The flow of study participants through the study protocol is shown in **Appendix 1**.

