20.3.1 Sample Size Rationale

The results of two prospective studies were used to inform the sample size estimation. The Endobronchial Valve for Emphysema Palliation Trial ("VENT Pivotal Trial", IDE#G020230, NCT00129584) was a multi-center, prospective, randomized, controlled study conducted at sites in both the United States and Europe to assess the safety and effectiveness of using the Zephyr EBV device for palliating symptoms associated with severe heterogeneous emphysema. Four hundred ninety two (492) participants were enrolled into the study and randomized to Zephyr EBV Treatment or medical management (control) [16,17]. The Chartis Pulmonary Assessment System study is a recently completed prospective post-market study that was conducted in Germany, The Netherlands, and Sweden. The primary objective of the study was to quantify the accuracy of the Chartis System when used to identify targeted treatment lobes as having or not having inter-lobar CV in patients with emphysema who were to be treated using endobronchial valves (26). The results of both the VENT Study and the Chartis System study showed that treatment effect with the endobronchial valve is correlated with lack of inter-lobar CV [16,17,25].

Patients in the VENT Study and in the Chartis Study who were considered to have little or no inter-lobar CV contributed the information used for the sample size estimate. Patients who have little or no lobar CV in the targeted treatment lobe are expected to be good responders to endobronchial valve treatment. For the sample

size estimate, a 'responder' was considered to be a study participant who had $\geq 15\%$ improved FEV₁ after EBV treatment.

Based on the results of these studies, the responder rate in the EBV Study Treatment Group is expected to be approximately 35% at 1 year. The responder rate for the control group is not expected to exceed 10% at 1 year. Assuming a two-sided 0.05 alpha level, study power of 90%, and 2:1 allocation random assignment, a sample size of 147 will be adequate to test for superiority.

The study sample size will be increased to 183 in order to allow for 20% lost to follow-up and incomplete data. Each study site will be allowed to enroll a maximum of 25 study participants.

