Study Design: This will be a multi-center, prospective, randomized, controlled study with EBV treatment statistically evaluated using Intent-to-Treat (ITT) analyses. A maximum of 183 ITT study participants, who meet study entry criteria, consisting of screening eligibility criteria, baseline eligibility criteria, and procedure eligibility criteria, were planned to be enrolled. A total of 190 study participants were enrolled. Safety and effectiveness of bronchoscopic lung volume reduction (BLVR) using the Pulmonx EBV will be evaluated at 1 year. An interim analysis designed to evaluate effectiveness for continuing crossover of control participants at 1 year to EBV treatment will be performed when 74 study participants have completed the 1-year follow-up. For study participants who have been treated with EBV, a secondary valve intervention such as valve removal, replacement, or adjustment may be considered during the study follow-up. Long-term data will be collected annually for EBV-treated study participants through 5 years. Per the regulatory plan agreed to with FDA, 1-year of follow-up is required pre-approval and the remaining 4 years of follow-up will be conducted post-approval.

Primary Effectiveness Endpoint

The percentage of study participants in the Endobronchial Valve (EBV) treatment arm who meet the threshold of \geq 15% improved forced expiratory volume in one second (FEV₁) as compared to the control arm at 1 year. Improved FEV₁ will be calculated by determining the percentage change for FEV₁ from baseline to 1-year post-procedure for individual study participants.

Secondary Effectiveness Endpoints

- 1) FEV₁: Difference between study arms in 'absolute change from baseline' for FEV1 at 1 year.
- 2) 6-Minute Walk Distance (6MWD): Difference between study arms in 'absolute change from baseline' for 6MWD at 1 year.
- 3) St. George's Respiratory Questionnaire: Difference between study arms in 'absolute change from baseline' for SGRQ score at 1 year.

Safety Endpoint

Evaluation of the short- and long-term adverse events profile during the treatment period, defined as the day of the study procedure until 45 days after the study procedure (short), and in the post-treatment period, defined as 46 days after the study procedure until the 1-year followup visit (long).

Additional Measures

- Treatment Lobe Volume Reduction (TLVR) for the treatment arm only
- Spirometry, including FEV₁, forced vital capacity (FVC) and the ratio of FEV₁/FVC

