The study hypothesis will be tested again at the end of the study. The Z-statistic will be calculated again, and by taking into account the interim analysis, will have a final critical boundary value of 2.004, per the nTerim program. If the trial is not stopped as a result of the interim analysis, then the final Z-statistic must be greater than or equal to 2.004 in order to reject the null hypothesis at the final analysis (at the overall 2-sided 5% significance level). Test statistic is "Z" as defined as:

$$Z = \frac{p_T - p_C}{\sqrt{p(1 - p)\left(\frac{1}{n_T} + \frac{1}{n_C}\right)}}$$

Where,

 p_T and p_C are the proportions of success for the primary endpoint in the treatment and control groups, respectively, *p* is the pooled estimate of the success rate, and

 n_T and n_C are the sample sizes obtained in the treatment and control groups,

respectively. Two sets of (p, p_T , p_C , n_T , n_C) will be obtained: one at the interim analysis and one at end of the study.

B. Analysis of the Secondary Effectiveness Endpoints

The following describes the analysis techniques to be used for each of the secondary endpoints. To control the family-wise type I error rate at 5%, the Hochberg step-up procedure will be utilized (Hochberg, 1988).

a. FEV₁

Difference between study arms in 'absolute change from baseline' for FEV1 score at 1 year. Descriptive statistics will include means, standard deviations and 95% confidence intervals. An analysis of covariance (ANCOVA) with factor of treatment and baseline FEV1 as a covariate will be used to test the difference between treatment arms. P-value will be adjusted for multiple imputation.

b. 6-Minute Walk Distance (6MWD)

Difference between study arms in 'absolute change from baseline' for 6MWD at 1 year. Descriptive statistics will include means, standard deviations and 95% confidence intervals. An analysis of covariance (ANCOVA) with factor of treatment and baseline 6MWD as a covariate will be used to test the difference between treatment arms. P-value will be adjusted for multiple imputation.

c. St. George's Respiratory Questionnaire (SGRQ)

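### The three secondary ANCOVAs pool one residual variance across arms in a 2:1 trial; a robust standard error would be a cheap, optional safeguard

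*SAP*

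**What the plan says.** SAP section IV.B tests three secondary endpoints, each as absolute change from baseline at 1 year: FEV₁ in litres, 6MWD in metres and SGRQ total score in points. The model is the same each time, with treatment and the endpoint's own baseline. For walking distance it reads "An analysis of covariance (ANCOVA) with factor of treatment and baseline 6MWD as a covariate will be used to test the difference between treatment arms".

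The three tests form a controlled family: "To control the family-wise type I error rate at 5%, the Hochberg step-up procedure will be utilized (Hochberg, 1988"). Each p-value is also adjusted for multiple imputation, and SAP section IX sets 20 imputed datasets. Neither section mentions a robust standard error, a separate residual variance by arm, a variance check or a fallback test. A single pooled variance is therefore implied by the model; it is not written down.

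Protocol section 5.0 fixes the allocation: "Random assignment will be conducted using an allocation ratio of 2:1", with EBV as the larger arm. The SAP's Study Design paragraph reports "A total of 190 study participants were enrolled". Protocol section 20.3.1 sets the planning rates: "the responder rate in the EBV Study Treatment Group is expected to be approximately 35% at 1 year" and "The responder rate for the control group is not expected to exceed 10% at 1 year". A responder there is someone whose FEV₁ improves by at least 15%. No SD, effect size or power is given for any secondary endpoint.

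**The concern.** With equal arms, pooling the variance leaves the standard error of a mean difference essentially right even when the two spreads differ. At 2:1 that protection is lost. The pooled variance is weighted towards the larger arm and is then applied to the smaller one. If EBV changes vary more than control changes, the standard errors and any model-based confidence intervals are too wide and power is lost. If EBV changes vary less, the tests reject too often and the 5% family-wise control no longer holds.

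A wider EBV spread is plausible. Some participants may respond strongly and others not at all. The protocol also anticipates pneumothorax in about one in five treated participants, and some valve removals, all of whom stay in the EBV arm under intention to treat. The documents do not quantify what this does to the spread of any secondary endpoint.

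**Working it through.** **The plan's own figure.** The documents state no power for the secondary tests, so only the primary sample size can be reproduced. The inputs, from Protocol 20.3.1, are 10% v 35%, two-sided 0.05, 90% power and 2:1.

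- Mean rate = (0.10 + 2×0.35)/3 = 0.2667.
- Uncorrected control n = [1.96√(3×0.2667×0.7333) + 1.2816√(2×0.10×0.90 + 0.35×0.65)]² / (2×0.25²) = 43.03.
- With continuity correction: (43.03/4)×[1 + √(1 + 6/(2×43.03×0.25))]² = 48.85, so 49 controls, 98 EBV and 147 in total. This matches the plan.
- 147/0.8 = 183.75, against 183 stated.

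**Arm sizes.** 190 at 2:1 is about 127 v 63. The split is derived, not stated.

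**Effect of pooling.** Set the control residual SD to 1 and the EBV residual SD to k. The baseline covariate is left out of the algebra.

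- Pooled SE² = [(126k² + 62)/188] × (1/127 + 1/63)
- True SE² = k²/127 + 1/63
- R = √(pooled SE²/true SE²)
- True two-sided size = 2×[1 − Φ(1.96R)]
- Power of a test that would have 80% with the correct SE = Φ(1.96 + 0.8416 − 1.96R)

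| k (assumed) | Pooled SE² | True SE² | R | True size | Power from 80% |
|---|---|---|---|---|---|
| 0.75 | 0.01678 | 0.02030 | 0.909 | 7.5% | (size inflated) |
| 1.00 | 0.02375 | 0.02375 | 1.000 | 5.0% | 80.0% |
| 1.25 | 0.03270 | 0.02818 | 1.077 | 3.5% | 75.5% |
| 1.50 | 0.04364 | 0.03359 | 1.140 | 2.6% | 71.5% |

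At 95 v 95, R is 1 for any k, which confirms that the 2:1 ratio drives the effect.

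**Which k fits the planning rates?** Let control FEV₁ percent change be normal with 10% above the threshold, so that 15% lies 1.2816 control SDs above the control mean. Let a share s of the EBV arm be shifted by d SDs, with d solved so that 35% exceed the threshold. Then k = √(1 + d²s(1−s)) and the mean difference is s×d control SDs.

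| s (assumed) | d | Mean difference | k | SE excess |
|---|---|---|---|---|
| 30% | 2.78 | 0.83 | 1.62 | 16.5% |
| 40% | 1.88 | 0.75 | 1.36 | 10.6% |
| 50% | 1.53 | 0.77 | 1.26 | 8.0% |
| 70% | 1.17 | 0.82 | 1.14 | 4.4% |
| 100% | 0.90 | 0.90 | 1.00 | 0% |

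The share cannot fall below (0.35 − 0.10)/0.90 = 27.8%, and k rises steeply near that limit. If 35% and 10% are instead read as true responder shares, with shifts of 1 / 2 / 3 SDs, k is 1.06 / 1.19 / 1.30 and the SE excess is 2.0% / 5.8% / 8.9%.

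**FEV₁ power under the same mixture.** The mixture fixes the mean difference as well as k. At 127 v 63 and alpha 0.05, power with the correct SE and with the pooled SE is 99.2% and 98.1% at s = 30%, and 99.5% and 99.3% at s = 50%. With only the 147 required participants (98 v 49) and Hochberg's strictest step (0.05/3), it is 92.6% and 85.5% at s = 30%, and 94.7% and 92.3% at s = 50%.

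**Simulation of the full ANCOVA** (127 v 63, baseline covariate, 10,000 runs per setting). Each pair is classical ANCOVA, then HC3.

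| k | Size | Power (80% target) |
|---|---|---|
| 0.75 | 7.2%, 5.0% | 84.0%, 78.3% |
| 1.00 | 5.1%, 4.8% | 79.6%, 79.0% |
| 1.25 | 3.1%, 4.5% | 74.8%, 78.7% |
| 1.50 | 2.8%, 5.2% | 71.2%, 79.2% |

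**The case against.** The strongest reply is that unequal variance is not shown. The 35% and 10% are rates of crossing a cut-point on a continuous measure. They do not establish two kinds of participant. A uniform shift of 1.2816 − 0.3853 = 0.90 SD with equal SDs reproduces both rates exactly, and nothing then changes. This stands.

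A reader might infer that the planned response rates make the EBV arm more variable, and that all three secondary tests will drop from 80% power to 70–75%. The documents do not support that. The 80% level appears nowhere in them. The mixture that produces the larger SD ratios also implies an FEV₁ effect large enough to keep power near 98–99% at full enrolment and alpha 0.05. The mixture is in percent change in FEV₁, whereas the secondary endpoint is in litres, and there is no responder rate or SD from which to carry it to 6MWD or SGRQ.

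The size figures also need care. They describe equal mean changes with unequal spread. If the valve did nothing for anyone, the spreads would be equal and the size would be 5%. Nothing in the documents points to a ratio below 1; the 0.75 row shows only that the error can run either way.

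Baseline-adjusted ANCOVA is a standard choice, and the planned SDs by arm would reveal a difference. But choosing the variance method after seeing those SDs would be data-driven. The imputation step gives no clear protection either. Missingness propensities are modelled separately by arm, so a difference in spread would be expected to carry into the imputed datasets. The calculations here leave out between-imputation variance and the zero change assigned to deaths.

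**Conclusion.** The point holds as a robustness gap. The secondary tests are valid as planned if the two residual variances are about equal. The plan neither justifies that nor provides for the alternative, and 2:1 allocation makes the tests sensitive to it. SD ratios from 1.0 to about 1.6 (at a 30% responder share) are compatible with the planning rates. At ratios up to 1.5 the standard error is up to 14% too large. An endpoint near 80% power could lose about 5 to 8 points at ratios of 1.25 to 1.5, while FEV₁ under the planned effect would lose about 1 point or less at full enrolment and alpha 0.05.

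All of this rests on assumed SD ratios and the derived 127 v 63 split. The primary Z-test is not affected. Severity is minor and the change is optional: no error or power loss has been demonstrated.

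**What to change.** Add one sentence to SAP IV.B: each secondary ANCOVA uses HC3 robust standard errors within each of the 20 imputed datasets before the results are combined. A residual variance for each arm with Kenward-Roger degrees of freedom is an acceptable alternative. State one of the two before the 1-year secondary comparisons are run. The baseline covariates, the imputation and the Hochberg procedure stay as they are.

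The cost is one model option. If the variances are equal, the simulated loss with HC3 was 79.6% − 79.0%, or about 0.7 points before rounding, so about 1 power point or less.

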	scale score	!		
COPD Assessment Test (CAT)	points		mean absolute change	
Transitional Dyspnea Index (TDI)	points		mean absolute change	
	<1 point im	proved	percent of participants	
Short Form (SF)-36 Health Survey	points		mean absolute change	
EQ-5D Health Survey	points		mean absolute change	
Other Measures				
Target Lobe Volume Reduction (TLVR)	milliliters		mean absolute change	

Table 4. Additional Effectiveness Endpoints

Other Measures		
Target Lobe Volume Reduction	milliliters	mean absolute change
(TLVR)		_
TLVR	percent	mean percent change
BODE Index	semi-quantitative scale	mean absolute change
	score	
	< 1, 0, > 1 change	percentage of participants
6MWD	percent	mean percent change
6MWD	Meters	mean absolute change at
		6 months
6MWD	25 meters improved	percentage of participants
6MWD	>54 meters improved	percentage of participants
6MWD – subjects stratified by	meters	mean absolute change
distance walked at baseline		
Borg Scale Dyspnea Score:	semi-quantitative scale	mean absolute change
Before 6MWD test	score	

Borg Scale Dyspnea Score:	semi-quantitative scale	mean absolute change
After 6MWD test	score	

b. Informational Purposes:

The following additional effectiveness endpoints will be measured in both treatment groups for informational purposes. Results will be described with summary statistics (see Table 5). These endpoints will be described for each treatment group separately and comparatively between groups by calculating mean change or difference in proportions, whichever is appropriate for the variable being analyzed.

Table 5. Informational Variables

Variable	Unit	Values Statistically Assessed
Maintenance Medications		
Bronchodilators	change in medication regimen	percentage of participants
Corticosteroids	change in medication regimen	percentage of participants
Antibiotics	change in medication regimen	percentage of participants
Anti-Inflammatories	change in medication regimen	percentage of participants
Pulmonary Rehabilitation	reported adherence to	percentage of participants
Compliance Diary	program	
Adherence to program	number of sessions / week	mean absolute number
Intensity of program	length of reported sessions	mean absolute number
EXACT-PRO Diary Entries	points	mean absolute number
Health Utilization	frequency of use	percentage of participants
Measures		
Lung Radiographic		
Features		
TLVR	volumetric change	mean percentage change
valve occlusion	qualitative assessment	percentage of participants
inter-lobar fissures	percent complete	percentage of participants

V. Adjustment for Potential Confounders

The covariates shown in Table 6 may be potentially influential with respect to the effectiveness endpoints. If any of these covariates are found to be out of balance between the groups (at the two-sided 0.10 level), they will be included in a multivariate analysis, along with an indicator of treatment group, to evaluate their potential effect on the study conclusions. A multivariate logistic regression model will be used for primary and secondary endpoints.

Table 6. Covariates

	Baseline	Procedure
Gender	X	
Age	X	
Clinical Site	X	
6MWD	X	
Patient-reported health status measures (e.g. SGRQ)	X	
Body Mass Index	X	
BODE Index	X	
Medication Use	X	
Residual Volume (RV)	X	
RV % Predicted	X	
Total Lung Capacity (TLC)	X	
TLC % Predicted	X	
RV/TLC	X	
IC/TLC	X	
Vital Capacity	X	
Forced Vital Capacity (FVC)	X	
FVC % Predicted	X	
FEV ₁	X	
FEV ₁ % Predicted	X	
FEV ₁ / FVC	X	
Lobar Volume	Х	
Lobar Destruction Scores	Х	
Ipsilateral DS Heterogeneity	X	
Severity of emphysema (GOLD classification)	X	
Comorbidities	X	
Target Treatment Lobe		Х
Treatment Group		Х

VI. Secondary Valve Procedures

Secondary valve procedures will be evaluated by examining the proportion of patients who undergo valve removal, valve replacement, or valve adjustment, and describing the reasons they occurred. Data for these study participants will be contrasted to data for study participants who did not receive a secondary valve procedure.

VII. Safety Analyses

Evaluation of the short- and long-term adverse events profile during the treatment period, defined as the day of the study procedure until 45 days after the study procedure (short), and in the post-treatment period, defined as 46 days after the study procedure until the 1-year follow-up visit (long). For the Control arm, the date of study procedure will be considered the date of the bronchoscopy assessment. Safety analyses will be performed by examining the percentage of patients that experiences adverse events. The rates and 95% exact confidence intervals will be presented on an event and on a per-patient basis. The percentage of subjects reporting adverse events occurring in at least 3% of subjects in either treatment arm will be compared using a Fisher's Exact test.

Adverse events will be categorized into clinically relevant groups (*e.g.:* stable pneumothorax with no intervention, pneumothorax resolved with chest tube insertion in less than 7 days,

prolonged air leak, etc.). Adverse events occurring in the treatment arm will be further categorized by severity and as device-related, procedure-related, or neither, and by those occurring during procedure hospitalization and those occurring post-discharge.

Rehospitalization rates will be reported by study arm on a Per-Patient (PPt) basis and on a Per-Event (PE) basis. In study participants who receive EBV treatment, adverse events will be evaluated by stratifying participants by use of conscious sedation and general anesthesia during the bronchoscopy procedure as well as evaluating number of valves received and sites EBV were placed.

VIII. Mortality

A Kaplan-Meier survival curve for each study arm will graphically display the time to death from the time of randomization and a log rank test will be used to compare Kaplan-Meier curves between study arms. A Cox proportional hazards model will be used to control for study site along with other significant co-variates as applicable.

IX. Patient Accountability and Missing Data

Every effort will be made to collect all data points in the study. The sponsor plans to minimize the amount of missing data by appropriate management of the prospective clinical trial, proper screening of study subjects, and training of participating investigators, monitors and study coordinators.

- The analysis for the primary endpoint will be performed by imputing missing data. Subject death prior to the 1-year visit date will be imputed as failure.
- For study participant FEV₁ data that is 'intermittent', missing outcomes will be imputed by linear interpolation using the FEV₁ value from the latest non-missing data point before the missed data point and the earliest non-missed data point after the missed data point.
- For study participants with truncated data (e.g. participants who drop out or are lost to follow-up), a multiple imputation strategy will be performed using the propensity score method. In brief, for a particular outcome, the propensities for study participants to have missing data (for each treatment group separately), modeled by logistic regression, are grouped into strata based on percentiles of the logistic propensity score model. Within a stratum, a study participant with a missing observation has an imputed value assigned by randomly choosing a value from among the study participants in the same stratum with non-missing observations. This procedure will be repeated 20 times on the entire dataset, resulting in 20 different 'complete' datasets allowing for estimation of the effect on the outcome of interest, accounting for missing data.

An additional analysis for the primary endpoint will be performed based on not imputing data. All partial data that is available on subjects who drop out during the course of the study will be included. In addition, sensitivity analyses such as worse-case or best-case imputation will be performed although it is recognized that they are biased.

Missing data for secondary endpoints will be imputed using the same methodology described above. Subject death prior to the 1-year visit date will be imputed baseline carried forward (0-point change).

- X. Comparison of Crossed-Over Control versus Study Treatment Outcomes
 - a. Effectiveness Outcomes

omparison based on paired Control versus EBV Treatment differences)				
Variable	Unit	Values Statistically Evaluated		
Forced Expiratory Volume (FEV ₁)	>15% improved	percentage of participants		
FEV ₁	Liters	mean absolute change		
FEV ₁	percent	mean percent change		
SGRQ Total Score	Points	mean absolute change		
mMRC Score	semi-quantitative	mean absolute change		
	scale score			
6-Minute Walk Distance	Meters	mean absolute change		
6MWD – subjects stratified by	meters	mean absolute change		
distance walked at baseline				
6MWD	25 meters	percentage of participants		
	improved			
DLco	percentage	mean absolute and percent change		
Residual Volume (RV)	liters	mean absolute and percent change		
Inspiratory Capacity (IC)	liters	mean absolute and percent change		
Total Lung Capacity (TLC)	liters	mean absolute and percent change		
RV/TLC	ratio	mean absolute change		
IC/TLC	ratio	mean absolute change		

Table 7. Effectiveness Endpoints for Control Arm Crossovers (comparison based on paired Control versus EBV Treatment differences)

The time-course of outcomes will be described. A paired t-test will be used to test the difference between treatment modalities for the quantitative outcomes. For binary outcomes, a McNemar test will be used to test the difference between the two treatment modalities.

b. Safety Outcomes

Evaluation of the short- and long-term adverse events profile of crossed-over participants during the second year of follow-up, when they have the EBV treatment, will be assessed as in Section VII above. Additionally, the time-course of occurrence of Serious Adverse Events (SAEs) will be contrasted and compared for the first year (Control Treatment) versus second year (EBV Treatment) periods. For those SAEs that could occur with either Control or EBV Treatment, a McNemar test-statistic will be used to quantify the magnitude of the difference between the two treatment modalities.

XI. Randomization Assignment Method

Study participants who are determined to meet screening, baseline, and procedure eligibility criteria will be randomly assigned to Study Treatment (EBV or Control). Random assignment will be performed using a stratified permuted block design, generated separately for each clinical site, with assignment stratified by anatomical site of the planned treatment (e.g. right lung or left lung). Mixed block sizes will be used.

XIII. Device Malfunction Analyses

Results of any device malfunctions and their sequelae are to be presented descriptively. The rate and exact 95% confidence intervals will be computed.

XIV. Statistical Software

The parametric and non-parametric analysis of variance and other primary analyses will be done using SAS, Version 9.2 or later or StatXact.

References

- 1. Meinert, C. (1986). *Clinical Trials: Design, Conduct, and Analysis*. Oxford University Press, New York.
- 2. Medical Devices Dispute Resolution Panel Meeting of September 6, 2001 (Panel Transcript)
- 3. Hochberg (1988) A sharper Bonferroni procedure for multiple tests of significance. Biometrika 75(4):800-802

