Means, standard deviations, medians, and confidence intervals will be reported for all continuous variables. Dichotomous variables will be reported as percentages and the numerator and denominator will be reported and defined.

II. Analyses of the Patient Populations

These analyses are intended to determine the similarity of two treatment groups and similarity of patients from different study sites with respect to important demographic or other variables, either known or suspected to have an influence on the outcome variables. The absence of similarity for any variable will identify that variable as a potential covariate in subsequent analyses.

- A. Comparability of Treatment Groups To assess the success of the randomization process, the demographic and prognostic variables measured at study entry will be compared between the Treatment and Control arms. Continuous variables will be compared with the two-sample t-test or the Wilcoxon two-sample rank test, and categorical variables will be compared with the Fisher's exact test or a Chi-square test. Comparability analyses will be done with two-sided tests with significance level of 0.05.
- B. Study Site Comparability –The appropriateness of pooling the data across study sites will be determined on a clinical basis, i.e., to ascertain if the sites used a common protocol, the sponsor adequately monitored the study to assure protocol compliance, and the data gathering and validation mechanisms were the same across all study sites (Meinert, 1986).

An analysis will be done to determine if the magnitude of the clinical effect of the primary outcome is maintained if sites and/or site by treatment interactions are included in an analysis of covariance model. We expect the majority of sites will show the treatment to be beneficial but statistically one would not expect all sites to show the treatment to be beneficial. For those sites with contrary results, an analysis will be attempted to determine what factors at those sites led to the result (See expert statistical testimony from Dispute Resolution Panel transcript September 6, 2001).

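### SAP Section V names logistic regression for three continuous secondary endpoints, and its 0.10 imbalance rule does not guarantee that the endpoint's own baseline is in the model

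*SAP*

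**What the plan says.** **Endpoints and main tests.** The SAP lists three secondary endpoints, each an absolute change from baseline compared between arms. For walking distance the wording is "Difference between study arms in 'absolute change from baseline' for 6MWD at 1 year". Table 3 gives the scales as litres, metres and points. SAP IV.B tests each one with a linear model that always contains the endpoint's own baseline; for FEV1, "An analysis of covariance (ANCOVA) with factor of treatment and baseline FEV1 as a covariate will be used". The Hochberg procedure covers these three tests.

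**Adjustment for confounders.** Section V takes the covariates of Table 6. If any are "found to be out of balance between the groups (at the two-sided 0.10 level"), then "they will be included in a multivariate analysis, along with an indicator of treatment group". The model is then named: "A multivariate logistic regression model will be used for primary and secondary endpoints". Baseline FEV1, 6MWD and SGRQ are ordinary rows of Table 6, and Section V forces no covariate in. The superseded plan in Protocol Appendix 19 named logistic regression without saying for which endpoints; the current sentence names the secondaries expressly.

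**Related text.** Section II compares the arms, and also patients from different sites. It says: "The absence of similarity for any variable will identify that variable as a potential covariate in subsequent analyses". For the comparison of arms, "Comparability analyses will be done with two-sided tests with significance level of 0.05". Section XI stratifies randomisation by clinical site and by lung side.

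**The concern.** A logistic model needs a yes/no outcome. Section V assigns one to three measured changes, so for the secondary endpoints the stated analysis cannot be run. Whoever performs it must choose a different model, or a cut-off, without guidance from the plan.

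The entry rule is a second weakness. When randomisation is sound, a between-arm difference at the 0.10 level arises by chance and does not show that the variable predicts outcome. The variable most likely to predict a change score is its own baseline. Section V treats that baseline like any other row of Table 6, although IV.B always includes it.

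At stake is the clarity of a supportive analysis meant to show whether the conclusions survive adjustment. The tests that decide the trial are not at stake.

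**Working it through.** Section V carries one number, the 0.10 level, so there is no figure of the plan to reproduce on this point. The sample-size calculation in Protocol 20.3.1 concerns the primary endpoint and is not involved.

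**1. Model against endpoint (SAP IV.B, Tables 3 and 4, Section V).**

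| Secondary endpoint | Scale | IV.B model | Section V model | Responder cut-offs in Table 4 |
|---|---|---|---|---|
| FEV1 change | litres | ANCOVA with baseline FEV1 | logistic | 12% (none in litres) |
| 6MWD change | metres | ANCOVA with baseline 6MWD | logistic | 25 m and 54 m |
| SGRQ change | points | ANCOVA with baseline SGRQ | logistic | 4 and 8 points |

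A trial fit of a binary logit to 190 simulated continuous changes was rejected by the software, because the outcome must lie between 0 and 1. The Table 4 responder versions, such as ">54 meters improved", do not fill the gap. They are additional endpoints, two of the three measures have two cut-offs each, and nothing links them to Section V.

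**2. The 0.10 rule.** Inputs: 190 enrolled at 2:1, so about 127 and 63; Table 6 has 27 rows, or 26 without Treatment Group.

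- Chance that a given baseline is unflagged: 1 − 0.10 = 0.90. Simulation at 127 against 63 gave 0.903.
- All three own baselines unflagged, if independent: 0.9³ = 0.729. All three flagged: 0.1³ = 0.001.
- Expected chance flags: 26 × 0.10 = 2.6. This is rough. Some rows (patient-reported measures, medication use, comorbidities, lobar destruction scores) cover several variables, and blocking within site makes a flag for site unlikely.

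**3. What the own baseline is worth.** The documents give no correlation r between baseline and change, so r is assumed. Leaving the baseline out of a linear model multiplies the standard error by 1/√(1 − r²):

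| Assumed r | 0.2 | 0.3 | 0.4 | 0.5 |
|---|---|---|---|---|
| Standard error ratio | 1.021 | 1.048 | 1.091 | 1.155 |

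That is roughly 2 to 15%. It applies only if Section V were run as a linear model without the own baseline.

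**4. Randomisation factors.** Site appears in the supportive analysis of II.B, in Table 6 and in the mortality Cox model of Section VIII. Lung side is a prespecified term in no model. It could enter only through Target Treatment Lobe in Table 6, if flagged, since every permitted target in Protocol 11.5 fixes the side. Adding it to an IV.B ANCOVA takes the residual degrees of freedom from 190 − 3 = 187 to 186. If it explained 2, 5 or 10% of residual variance (assumed), the standard error would be multiplied by √(1 − R²) = 0.990, 0.975 or 0.949.

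**The case against.** The strongest reply is that the intent is plain: the IV.B ANCOVA with extra covariates, for an analysis that decides nothing. Section V says flagged covariates join the treatment indicator; it does not say that the IV.B baseline is removed. On that reading nothing is lost. This stands as to consequence, and it is why the point is minor. It does not rescue the sentence, which expressly names logistic regression for the secondaries.

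A reader might infer more than the documents support:

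- **That the main secondary tests omit the baseline or are invalid.** They do not and are not; IV.B includes it in all three.
- **That Section V adjusts for less than the main analysis.** About 2.6 chance flags are expected, against one covariate in each ANCOVA. Only the possible absence of the own baseline is supported.
- **That the 0.10 test is the only route by which a variable can become a covariate.** Section II also covers dissimilarity between sites, so a Table 6 variable can become a potential covariate without a between-arm flag, although Section II does not tie this to the Section V model.
- **That 0.05 in II.A contradicts 0.10 in V.** Any between-arm difference significant at 0.05 also passes 0.10.
- **That power would be lost by dichotomising.** The SAP nowhere dichotomises the secondary endpoints for their tests.
- **That pooled site would need a conditional logistic model for the primary.** A pooled site with no responder makes only its own site term non-finite; the treatment estimate is still obtained.

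**Conclusion.** The point holds and is minor. As written, the Section V analysis of the three secondary endpoints cannot be fitted, and no text supplies the missing dichotomy. Its entry rule responds to chance imbalance, and read literally it leaves an endpoint's own baseline unflagged, and so not required, in about 90% of trials. The 90% follows from the 0.10 level and assumes sound randomisation. Any precision figure for the own baseline (2 to 15%) or for lung side rests on assumed correlations or variance shares.

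The pooled Z test of the primary endpoint and the Hochberg-controlled ANCOVAs remain valid, and the primary conclusion does not depend on Section V. Adding lung side to those ANCOVAs would be an improvement; its absence does not make them wrong.

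**What to change.** 1. In Section V, keep logistic regression for the binary primary endpoint only. For the changes in FEV1, 6MWD and SGRQ, name the IV.B ANCOVA (a linear model) plus covariates.
2. Always retain the endpoint's own baseline, with baseline FEV1 for the primary. Replace the 0.10 entry test with a short fixed list that includes the randomisation factors: lung side, and site pooled as in II.C. The Section II sentence on potential covariates can stay, since it only marks candidates.
3. Separately, add lung side to each secondary ANCOVA in IV.B.
4. Leave the primary Z test and its 2.571 and 2.004 boundaries unchanged.

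The cost is a few sentences in Section V and one degree of freedom in each secondary ANCOVA. The sample size and data collection do not change. If only one change is made, correcting the model sentence and retaining the own baseline removes the core defect. As all 190 participants are enrolled, the change should be dated before the final 1-year comparison is run.
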